141 Note that the above permanent datasets include all IXT1 patients, but the analysis was limited to
142 the cohort of interest for this abstract.

143
144
145
146
147
148
149
150
151
152
153

Objective #1: Define the cohort of interest

1. 197 patients with basic-type IXT with largest preoperative exodeviation between 15 and 40 PD by PACT at remote distance, distance, or near (101 in BLR group, 96 in R/R group)

Technical plan

1. Limit the patient-level dataset ROSTER to patients where the STRATUM variable from tblStratum, the variable used to stratify the randomization, = 'Basic IXT with 15-40PD angle'

Dataset used: ROSTER

154 **Objective #2: Compare the cumulative probability of surgical failure BY 3 years between**
 155 **BLR and R/R treatment groups (primary outcome)**

- 156 1. Define the outcome
 157 2. Obtain masked exam records
 158 3. Determine whether exotropia failure criterion was met for each masked exam
 159 4. Determine whether constant esotropia failure criterion was met for each masked exam
 160 5. Determine whether stereoacuity failure was met for each masked exam
 161 5. Determine whether patient was reoperated or underwent treatment with botulinum toxin
 162 6. Calculate surgical failure at patient level and set timing variable for survival analysis (time to
 163 failure or censoring time)
 164 7. Get cumulative probability of surgical failure by 3 years for each treatment group – from K-
 165 M
 166 8. Compare cumulative probability of surgical failure by 3 years between treatment groups
 167 using a two-sided Z-test
 168 9. Calculate the treatment group difference (and 95% CI) in the cumulative probability of
 169 surgical failure by 3 years
 170

171 **Technical plan**

- 172 1. Define the outcome.

173 **Failure** = ANY of the following criteria are met at masked exam occurring between 6 months
 174 and 3 years after randomization:
 175

- 176 1. **Exotropia** at distance OR near at any time during the exam (i.e., can be constant or
 177 intermittent; determined by a cover/uncover test) with a magnitude of atleast 10 PD by
 178 SPCT, confirmed by a retest
 179 2. **Constant esotropia** at distance OR near (determined by at least 3 cover/uncover tests—one
 180 must be before any dissociation) with a magnitude of atleast 6 PD by SPCT, confirmed by a
 181 retest
 182 3. Decrease in Preschool Randot near **stereoacuity** atleast 2 octaves (atleast 0.6 log arcsec)

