- 285 • Output survival probabilities and confidence intervals to a dataset
- 286 • Create failure estimates and confidence intervals

```

287
288 /*****
289     PERFORM K-M ANALYSIS
290     PRIMARY OUTCOME
291     CUMULATIVE PROBABILITY OF SURGICAL FAILURE
292     NOTES FOR K-M SURVIVAL ANALYSIS
293     NUMBER AT RISK = NUMBER AT RISK GOING INTO THE VISIT
294                     (E.G. LAST PERSON AT 3 MONTHS BEFORE 6 MONTHS)
295     OUTSURV OPTION IN PROC LIFETEST STATEMENT CREATES AN OUTPUT DATASET
296     THAT CONTAINS SURVIVAL ESTIMATES AND CONFIDENCE LIMITS.
297     PARENTHETICAL IN TIME STATEMENT INDICATES WHAT CENSORING VALUE IS
298 *****/
299
300 %sort (roster, trtgroup);
301 proc lifetest data = roster method=km  outsurv=failresults plots=none alpha=.05;
302     time failtime*fail(0);
303     by trtgroup;
304     title2 'K-M Survival Analysis for Surgical Failure';
305 run;
306
307 proc print data = failresults;
308     title2'Review Output Dataset from K-M Survival Analysis for Surgical Failure';
309 run;
310
311 data failresultCIs;
312     set failresults;
313
314     /* create failure estimates (rather than survival)*/
315     failure = 1 - survival;
316     failureLCL = 1 - SDF_UCL;
317     failureUCL = 1 - SDF_LCL;
318
319     /* limit to records where the survival estimate has changed
320        (i.e. records where the CI is not null) */
321
322     if SDF_LCL NE . then output;
323
324     label failure = 'Cum. probability of surgical failure';
325     label failureLCL = 'Lower limit of CI for surgical failure';
326     label failureUCL = 'Upper limit of CI for surgical failure ';
327
328 run;
329
330 %sort (failresults, trtgroup);
331 proc print data = failresultCIs;
332     by trtgroup;
333     title2'Review Output Dataset from K-M Survival Analysis for Surgical Failure';
334 run;

```

- 336
- 337 **9.** Compare cumulative probability of surgical failure by 3 years for each treatment group using
- 338 a Z-test code
- 339

340 See below—combined with step #10.

341 **10. Calculate the treatment group difference (and 95% CI) in the cumulative probability of**
342 **surgical failure by 3 years.**

```
343 /* Manually enter cumulative probabilities and standard error from K-M into short
344 program to calculate Z-score, its corresponding P value, the treatment group
345 difference and 95% CI */
346
347 data check;
348     input probblr seblr probrr serr;
349     datalines;
350     0.4594 0.0518 0.3731 0.0520
351 ;
352 run;
353

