354 data check;
355     set check;
356     diff = probblr - probrr;
357     sumofsquaredse = sqrt (seblr**2+serr**2);
358     cilower = diff - (1.96*sumofsquaredse);
359     ciupper = diff + (1.96*sumofsquaredse);
360     zscore = diff/sumofsquaredse;
361     pvalue = 2*(1 - probnorm(zscore));
362 run;
363
364 proc print data = check noobs;
365     var analysis probblr seblr probrr serr sumofsquaredse diff cilower ciupper zscore
366     pvalue;
367     title'Calculate CIs and P values;
368 run;
369
370
371
372 Datasets used: MASKEDEXAMS, BASELINE, ROSTER, tblIXT1Treatused (SQL)
```

373 **Objective #3: Compare the binomial proportion of surgical failure AT 3 years between**
374 **BLR and R/R treatment groups**

- 375
- 376 1. Define the outcome
 - 377 2. Determine whether exotropia failure criterion was met at the 3-year masked exam
 - 378 3. Determine whether constant esotropia failure criterion at the 3-year masked exam
 - 379 4. Determine whether stereoacuity failure criterion was met at the 3-year masked exam
 - 380 5. Determine whether patient was reoperated or underwent treatment with botulinum toxin,
381 regardless of whether he/she first met one of the three surgical failure criteria
 - 382 6. Create surgical failure at 3 years
 - 383 7. Calculate binomial proportion, treatment group difference, and 95% exact confidence
384 intervals
- 385

386 **Technical plan**

- 387 1. Define the outcome
- 388 • The secondary outcome of surgical failure AT 3 years (not BY 3 years) is defined as
389 follows:

390 **Failure** = ANY of the following criteria are met atthe3-yearmaskedexam:

- 392 1. **Exotropia** at distance OR near at any time during the exam (i.e., can be constant or
393 intermittent; determined by a cover/uncover test) with a magnitude of atleast 10 PD by
394 SPCT, confirmed by a retest
 - 395 2. **Constant esotropia** at distance OR near (determined by at least 3 cover/uncover tests—
396 one must be before any dissociation) with a magnitude of atleast 6 PD by SPCT,
397 confirmed by a retest
 - 398 3. Decrease in Preschool Randot near **stereoacuity** atleast 2 octaves (atleast 0.6 log arcsec)
399 (*see Table 3*) from the enrollment measurement, or to nil, confirmed by a retest (*see*
400 *Table 1* from objective #2)
- 401

402 Patients will also be considered a surgical failure at 3 years if they undergo **reoperation** or
403 treatment with botulinum toxin at any time during the study.

404

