- 450 4. Compare cumulative probability of reoperation by 3 years for each treatment group using
451 two-sided Z-test
- 452 5. Calculate the treatment group difference (and 95% CI) in the cumulative probability of
453 reoperation by 3 years.
454

455 **Technical Plan**

- 456 1. Define the outcome
457
458
459 Reoperation or botulinum toxin treatment at any time during the study, including cases where
460 reoperation was completed after surgical failure was met and cases where reoperation occurred
461 without surgical failure first having been met (i.e. against protocol).

- 462 2. Determine whether patient was reoperated or underwent treatment with botulinum toxin,
463 regardless of whether he/she first met one of the three surgical failure criteria
464 • Use reoperation outcome and time to reoperation variables created for objective #2.
465
- 466 3. Get cumulative probability of reoperation by 3 years for each treatment group – from K-M
- 467 4. Compare cumulative probability of reoperation by 3 years for each treatment group using Z-
468 test
- 469 5. Calculate the treatment group difference (and 95% CI) in the cumulative probability of
470 reoperation by 3 years.
471

472 Repeat steps #8 - #10 for objective #1 using the reoperation outcome and time to reoperation
473 variables.
474

475 **Objective #5: Compare 3-year control and PACT values between BLR and R/R treatment**
476 **groups**

- 477
- 478 1. Define the outcomes
 - 479 2. Define the cohort
 - 480 3. Compare mean 3-year outcomes between treatment groups

481
482 **Technical Plan**

- 483 1. Define outcomes.
- 484 a. PACT size (distance and near)
 - 485 • Code according to size and type
 - 486 ○ Exodeviations will be coded as positive values (same as in database)
 - 487 ○ Esodeviations will be changed to negative values
 - 488
 - 489 b. Exotropia Control (distance and near)
 - 490 ○ For both distance and near, create numeric values for exotropia control where ‘not
 - 491 applicable’ will be assigned a score of 0, the same as the score for a pure phoria.
 - 492 Note that ‘not applicable’ was entered on the form when no exodeviation was present.
 - 493
 - 494

Table #1: Intermittent Exotropia Control Scale Scoring

5	Constant Exotropia
4	Exotropia > 50% of the 30-second period before dissociation
3	Exotropia < 50% of the 30-second period before dissociation
2	No exotropia unless dissociated, recovers in >5 seconds
1	No exotropia unless dissociated, recovers in 1-5 seconds

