0	No exotropia unless dissociated, recovers in <1 second (phoria)
Not applicable	No exodeviation present

[figure not shown]
[figure not shown]
495
496 For both PACT and control outcomes, use the 3-year visit data for all patients who completed
497 the 3-year visit, regardless of what treatment(s) were received or if the patient had undergone
498 reoperation.

- 499
- 500 2. Limit the analysis to patients who completed the 3-year visit.
 - 501
 - 502 3. Compare mean 3-year outcome between treatment groups using ANCOVA model.

```
503 proc genmod data = roster;  
504 class trtgroup;  
505 model controlnumdi_36 = trtgroup controlnumdi_0;  
506 where comp_36 = 1;  
507 title 'Comparison of 3-year distance control between treatment groups';  
508 run;  
509
```

510 **Datasets used: MASKEDEXAMS, ROSTER**

511 **Version History**

Version Number	Author	Approver	Effective Date	Revision Description
1.0	[name]	[name] 	1-19-17	Original SAP for outcome data included in submitted AAPOS abstract (note that the analyses were specified in the protocol).
1.1	[name]	[name] 	3-1-17	For the purpose of the AAPOS presentation, added section 1.8 on secondary analyses of 3-year exotropia control and 3-year angle magnitude (note that these analyses were specified in the protocol).

512

1
2
3
4
5
6
7
8
9
10
11
12
13
14
15
16
17
18
19
20
21

IXT1 Primary Manuscript on Basic Primary Cohort

Statistical Analysis Plan for Secondary Outcomes Not Covered in Previous Analysis Plans

May 30, 2018

Revision History

VERSION NUMBER		AUTHOR	APPROVER	EFFECTIVE DATE	REVISION DESCRIPTION (INCLUDING SECTIONS REVISED)
SAP	Protocol				
1.0	5.0 6-21-17	[name]	[name]	5/14/18	Initial version
1.1	5.0 6-21-17	[name]	[name]	6/11/18	In the SAS code on line 425 that creates a p value using a z-score, changed to using the absolute value of the z score (instead of the z score itself) to account for situations in which a two-sided test yields a negative z-score.

22 **Important Notes:**

23 The primary analysis and many of the secondary analyses were completed for several abstracts and
24 presentations preceding completion of the primary manuscript. Below is a list of outcomes which are
25 documented in previous analysis plans plus outcomes which are covered herein.

26 **AAPOS Abstract and Presentation 2017**

- 27 • **Surgical failure by 3 years (primary outcome) (reabeled “suboptimal surgical outcome” at 3**
- 28 **years)**

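### The p-value line in the 2017 SAP omits the absolute value of z and is reused for reoperation, so any outcome with a higher R/R rate returns a p-value above 1

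*SAP*

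**What the plan says.** The 2017 SAP (v1.1, effective 3-1-17) plans to compare the Kaplan-Meier failure probabilities by 3 years "using a two-sided Z-test" (Objective #2, summary list). It plans a "two-sided Z-test" for reoperation by 3 years as well (Objective #4, summary list).

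The code under Objective #2, step 10, carries this out in three lines:

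- the difference: "diff = probblr - probrr"
- the test statistic: "zscore = diff/sumofsquaredse", where the divisor is the square root of the sum of the two squared standard errors
- the p-value: "pvalue = 2*(1 - probnorm(zscore", with closing brackets omitted here and no absolute value

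The figures entered into that code are "0.4594 0.0518 0.3731 0.0520" (BLR probability, its SE, R/R probability, its SE).

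Objective #4 gives no code of its own. It says: "Repeat steps #8 - #10 for objective #1 using the reoperation outcome and time to reoperation" variables. Objective #1 only defines the cohort; steps 8 to 10 exist only under Objective #2, so those must be the steps meant.

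The 2018 SAP covers secondary outcomes that earlier plans did not. Its v1.1 revision note (6/11/18) says that the matching line there was "changed to using the absolute value of the z score (instead of the z score itself"), because a two-sided test can produce a negative z. The corrected block lists three outcomes: exotropia, constant esotropia and stereoacuity failure. The notes at the front of the 2018 SAP list surgical failure by 3 years and reoperation by 3 years among the outcomes documented for the 2017 presentation. They add that those variables were rerun on post-closeout data in August 2017.

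**The concern.** Twice the upper tail area beyond z is a two-sided p-value only if z is not negative. Because the difference is BLR minus R/R, z is negative whenever R/R does worse, and the line then returns a value between 1 and 2.

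If the output is compared mechanically with 0.05, the procedure can reject in one direction only. A real excess of failure or reoperation under R/R could never be declared significant from this p-value, however large it was.

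That direction was not far-fetched when the plan was written. Protocol 6.6 expects R&R patients to fail earlier, mainly through overcorrection. One sentence in Protocol 6.7 assumes 25% failure with BLRrec and 50% with R&R, although the next paragraph reverses those figures.

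The sponsor recognised the fault and recorded a correction, but in the plan for the post hoc cause-specific outcomes. In the documents as provided, one trial has two p-value formulas for the same test, and the faulty one is attached to the primary outcome.

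**Working it through.** **Inputs.** From the 2017 SAP, Objective #2, step 10: BLR 0.4594 (SE 0.0518), R/R 0.3731 (SE 0.0520). Group sizes from 2017 SAP 1.2: 101 BLR, 96 R/R. The documents print no p-value, so there is no stated figure to reproduce; the code was run as written.

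**Entered primary figures.**

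- diff = 0.4594 - 0.3731 = 0.0863
- SE = sqrt(0.0518² + 0.0520²) = 0.0734
- 95% CI = 0.0863 ± 1.96 × 0.0734 = -0.0576 to 0.2302
- z = 0.0863 / 0.0734 = 1.1758 (unrounded SE)
- p as coded = 2 × (1 - Φ(1.1758)) = 0.2397; with |z| it is also 0.2397

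**Same figures with the arms swapped.** z = -1.1758. The code gives 1.7603; with |z| the answer is 0.2397.

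**General result.** For z < 0, 1 - Φ(z) = Φ(|z|), so the coded value is 2Φ(|z|) = 2 - 2(1 - Φ(|z|)), that is, 2 minus the correct p. The coded value is below 0.05 only if Φ(z) > 0.975, that is, z > 1.96. Used mechanically, the line is therefore a one-sided test at 2.5% against BLR, with no possibility of rejecting against R/R.

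| z | p as coded | correct p |
|---|---|---|
| -0.5 | 1.3829 | 0.6171 |
| -1.0 | 1.6827 | 0.3173 |
| -1.96 | 1.9500 | 0.0500 |
| -2.5 | 1.9876 | 0.0124 |
| -3.5 | 1.9995 | 0.0005 |

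**Reoperation.** No rates are given. The rates below are assumptions for illustration only, with binomial SEs sqrt(p(1 - p)/n) at n = 101 and 96.

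| BLR | R/R | z | p as coded | correct p |
|---|---|---|---|---|
| 5% | 10% | -1.3326 | 1.8173 | 0.1827 |
| 5% | 15% | -2.3581 | 1.9816 | 0.0184 |
| 10% | 20% | -1.9773 | 1.9520 | 0.0480 |

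In the last two rows the correct test is significant at 5% and the coded value is not below 0.05.

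**The case against.** Several points limit the weight of this, and most of them stand.

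- No figure in the documents is shown to be wrong. The entered primary inputs give a positive z, and the p-value is the same either way.
- The confidence limits are correct for either sign, so an interval excluding zero would still show a difference against R/R. The fault lies in one output line; the test described in the text is sound.
- A p-value above 1 is impossible on its face and can be recovered as 2 minus the printed value. It cannot create a false positive.
- The listing may not be the program that was run. Its print step asks for a variable named analysis that the data step never creates. On that view the two-sided wording governs and the code only illustrates it.
- The rerun passage in the 2018 SAP says the variables were recreated. It does not say that this block was rerun unchanged. The dataset counts are the same in both plans (277, 1344 and 265 records), and nothing suggests that the 8.6-point primary difference changed sign.

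The argument fails as a reason to leave the line alone. The direction of the reoperation result cannot be told from the documents. The 2018 correction does not reach the primary outcome or reoperation, because that plan is confined to outcomes not covered before. The August 2017 rerun also came before the June 2018 correction.

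**Conclusion.** The concern holds. As written, the 2017 code does not deliver the planned two-sided p-value when the R/R rate is higher: it returns a value between 1 and 2, equal to 2 minus the correct one. This applies to the primary outcome directly and to reoperation through Objective #4, on the only workable reading of its cross-reference.

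The practical effect is limited. The primary result as entered (z = 1.18, p = 0.24, 95% CI -0.058 to 0.230) is right. For reoperation the effect depends on the sign of a difference that is not given. The main exposure is a missed significant excess under R/R, and only if the impossible p-value and the interval are both overlooked.

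The conclusion rests on the documents as provided. They contain no later version of the 2017 plan and do not show which code produced the post-closeout results.

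**What to change.** In the 2017 SAP, Objective #2, step 10, put abs() around zscore in the p-value line, as was done in the 2018 SAP. State that the corrected line serves Objectives #2 and #4, and record the change in the 2017 version history.

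In Objective #4, change the cross-reference for steps 8 to 10 from objective #1 to objective #2.

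Confirm that the post-closeout p-values for the primary outcome and for reoperation came from the corrected form, or recompute them from the Kaplan-Meier estimates and standard errors.

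The cost is one code token, one corrected cross-reference and one check. No data, sample size or design element changes.

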144 • If prism is currently prescribed, ocular alignment testing should be performed *without*
145 prism.
146 • If deliberate overminus** is currently prescribed, ocular alignment testing should be
147 performed in trial frames *without* the overminus component of the prescription.
148 9. Control of exodeviation assessment at distance and near #3 (repeat) (*see item #2*)
149 • The third control testing is to be performed immediately after the previous testing—it
150 does not need to be performed before dissociative testing and no 10-minute break is
151 needed.
152 • The same examiner should assess IXT control each of the three different times that
153 control is assessed during the annual study visit.
154 10. Cycloplegic refraction (*7-year visit only*)
155 • If the current correction at the 7-year visit is not optimal based on the cycloplegic
156 refraction, new spectacles should be prescribed.

157
158 *Testing procedures are performed as described in section 2.5 *unless otherwise specified above*.

159
160 **Deliberate overminus lenses = lenses that yield > 0.50 D *more minus* spherical equivalent (SE)
161 than the refraction SE.

162
163 All testing procedures are assessed unmasked.

164
165 At each annual visit, data on treatments used or prescribed, current refractive correction, and the
166 last refraction will be recorded.

167 **Treatment**

168
169 Treatment in the extension study is at investigator discretion, including non-surgical treatment
170 and reoperation.

171 **Costs**

172
173 The parent/guardian of each subject will be compensated \$50 per visit for completion of each
174 annual protocol-specified follow-up visit (4-, 5-, 6-, 7-, and 8- year) for a maximum of \$250. If
175 there are extenuating circumstances, and the subject is unable to complete the annual study visits
176 without additional funds due to travel costs, additional funds may be provided.

177
178 In the additional 5 years of follow up provided for by Protocol Amendment II (>3 years to 8
179 years after randomization), the study will pay for visits specific to the research study, but will not

180 pay for usual care visits that would occur whether or not the child was in the study. The cost of
181 usual care visits will be the parent(s) or their insurance company's responsibility.
182

183 Treatment is at investigator discretion and is not part of this protocol. Any costs associated with

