- 69 • Patients who appear to have met surgical failure criteria by initial testing but who did not
70 complete all required retesting for that criteria are retained in the analysis and are
71 considered not to have met surgical failure criteria.
- 72 • Patients who have not yet met surgical failure are considered to retain their non-failure
73 status throughout any subsequent consecutive missed visit(s) until this status is
74 potentially changed at a completed visit. For example, a patient who is a non-failure at a
75 completed 1 year visit, misses the 18-month and 2-year visits, and is classified as a
76 failure at a completed 30-month visit, the non-failure status from the 1 year visit is
77 maintained until the 30-month visit.

78
79 **1.6 Secondary Analysis -- Surgical Failure at 3 Year Time point**

80 The binomial proportion of patients who meet surgical failure criteria *at* the 3 year visit (as
81 opposed to *by* the 3 year visit) will be estimated for each treatment group and compared using
82 Fisher's exact test.

83
84 Patients who do not return for the 3 year visit will not be included in the analysis, including
85 patients who met surgical failure criteria at an intermediate visit or were reoperated. Patients

86 who complete the visit will be classified based on their status at 3 years, regardless of whether
87 they met surgical failure criteria at an earlier time point, unless they have been re-operated (or
88 treated with botulinum toxin), in which case they will be classified as a surgical failure.

89 The potential for bias in this treatment group comparison is recognized. Once a patient has met
90 the clinical criteria for surgical failure criteria at an interim follow up visit, the decision to
91 reoperate—and thus permanently classify the patient as a surgical failure for the analysis at 3
92 years—is at the discretion of an unmasked investigator and therefore could be related to
93 treatment group. To assist in assessing for potential bias, the association between treatment
94 group and reoperation in those meeting surgical failure criteria will be evaluated.
95

96 **1.7 Secondary Analysis -- Reoperation by 3 Years**

97 The cumulative proportion of patients undergoing reoperation or treatment with botulinum toxin
98 by 3 years will be obtained using the Kaplan-Meier method and compared between treatment
99 groups using the Z test. This outcome will include all cases of reoperation—cases where

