- Evaluate all masked exams. *Even though only the first masked exam where failure criteria is met is relevant to the primary outcome, save stereoacuity failure criteria flag in a masked-exam-level dataset because interested in whether this criteria is met at the 3 year visit also, and may also be interested in other visits as well.*
- 250
- 251
- 252
- Determine the best stereoacuity at the baseline visit. Note that stereo was to be retested unless the patient scored 40 arcsec on the initial test.
- 253
- 254
- Compare masked exam initial to best baseline stereo and determine whether meets criteria for 2 or more level worsening (use Table 1 under step 1).
- 255
- 256
- If the worsening was not confirmed by the retest or the retest was not completed, the patient was considered not to have met stereoacuity failure criteria.
- 257
- 258
- 259
6. Determine whether patient was reoperated or underwent treatment with botulinum toxin
- 260
- Get treatment used records from all visits, regardless of whether a masked exam was completed
- 261
- 262
- If REOPERATION = 1 for any treatment used, and set patient-level reoperation to 1 and capture reoperation date
- 263
- 264
- 265
7. Calculate surgical failure at patient level and set timing variable for survival analysis (time to failure or censoring time)
- 266
- Loop through masked exam records for each patient and determine the first masked exam at which any of the three objective failure criteria were met.
- 267
- 268
- In patient-level dataset:
 - If reoperation occurs and surgical failure has not been met (either not at all or not by the time of reoperation), failure = 1 and failure time = months between surgery and reoperation
 - If one of the surgical failure criteria were met, either before reoperation or in a patient who is not reoperated, failure = 1 and failure time is based on visit type (e.g. 6 months, 12 months, etc.) or months between failure and surgery if failure occurs at an unspecified visit
 - If patient does not meet surgical failure and is not reoperated, failure = 0 and failure time is based on type of last completed visit (e.g. 6 months, 12 months, etc.)
- 269
- 270
- 271
- 272
- 273
- 274
- 275
- 276
- 277
- 278
- 279
- 280
8. Get cumulative probability of surgical failure by 3 years for each treatment group – from Kaplan-Meier survival analysis
- 281
- 282

- 283 • Run Kaplan-Meier survival analysis using proc lifetest, and specifying the method as
- 284 Kaplan-Meier.

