405 The outcome is assessed only in patients who complete the 3-year visit. To prevent biasing the
406 estimates, patients who were reoperated before being lost to follow up will not contribute to the
407 analysis (even though their surgical failure at 3 years status would have been permanently set
408 when they were reoperated, if had they completed the 3-year visit).

- 409
 - 410 2. Determine whether exotropia failure criterion was met at the 3-year masked exam
 - 411 • Created as part of objective #2 -- get data from 3-year visit record from
412 MASKEDEXAMS dataset.
 - 413
 - 414 3. Determine whether constant esotropia failure criterion at the 3-year masked exam
 - 415 • Created as part of objective #2 -- get data from 3-year visit record from
416 MASKEDEXAMS dataset.
- 417

- 418 4. Determine whether stereoacuity failure criterion was met at the 3-year masked exam
419 • Created as part of objective #2 -- get data from 3-year visit record from
420 MASKEDEXAMS dataset.
421
- 422 5. Determine whether patient was reoperated or underwent treatment with botulinum toxin,
423 regardless of whether he/she first met one of the three surgical failure criteria
424 • Use patient-level reoperation flag and reoperation date created for objective #2.
425
- 426 6. Create surgical failure at 3 years
427 • For patients who completed the 3-year visit:
428 ○ Code as 1 if any of the three surgical failure criteria are met at 3 years or if
429 reoperation occurred at any time.
430 ○ Otherwise code as 0
431
- 432 7. Calculate binomial proportion for each treatment and compare between treatment groups
433 with a Fisher's exact test. Calculate treatment group difference, and 95% exact confidence
434 intervals.
435

```
436 proc freq data = roster;  
437     tables trtgroup*failat36;  
438     exact fisher riskdiff;  
439     where vis_36 = 'Completed';  
440     title1 'Comparison of Crude % with Failure ***AT*** 3 Years';  
441 run;
```

442 **Datasets used: MASKEDEXAMS, ROSTER**

443 **Objective #4: Compare the binomial proportion with reoperation by 3 years between BLR**
444 **and R/R treatment groups**
445

- 446 1. Define the outcome
- 447 2. Determine whether patient was reoperated or underwent treatment with botulinum toxin,
448 regardless of whether patient first met one of the three surgical failure criteria
- 449 3. Get cumulative probability of reoperation by 3 years for each treatment group – from K-M

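### The coding of failure AT 3 years counts reoperation or botulinum toxin with no upper date, although the protocol now allows follow-up, and discretionary reoperation, to 8 years

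*SAP*

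**What the plan says.** **Failure AT 3 years (2017 SAP).** Section 1.6 states the intention: children "who complete the visit will be classified based on their status at 3 years, regardless of whether" they failed earlier, except that a reoperated or toxin-treated child is a failure. Objective #3 step 1 words that exception as reoperation or "treatment with botulinum toxin at any time during the study". Step 6 codes 1 if any of the three criteria is met at 3 years or if "reoperation occurred at any time".

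**Source of the flag.** Objective #2 step 6 instructs: "Get treatment used records from all visits, regardless of whether a masked exam was completed". A reoperation in any of these records sets the patient-level flag, and its date is kept. Objective #3 step 5 carries both forward: "Use patient-level reoperation flag and reoperation date created for objective #2". Step 6 does not use the date.

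**Extension (Protocol Amendment II, February 2015).** Optional visits run from 4 to 8 years. "Treatment in the extension study is at investigator discretion, including non-surgical treatment" and reoperation. "At each annual visit, data on treatments used or prescribed, current refractive correction, and the" last refraction are to be recorded.

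**Resolution outcomes (2018 SAP).** Section 1.5 and Objective #4 list the absence of reoperation or toxin among items to be met at the 3-year visit. The version with no previous failure excludes any child with a suboptimal outcome at any time, while the same objective names suboptimal outcome *by* 3 years as its input. The tabulation of 3-year status in section 1.7 uses reoperation before 3 years.

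**The concern.** An outcome labelled AT 3 years should depend only on what had happened by the 3-year exam. The three objective criteria meet that test, because they are read from the 3-year masked exam. The reoperation component has no such limit. The rule was written when the protocol already provided for follow-up beyond 3 years, without the requirement in Protocol sections 4.1 and 4.7 that failure criteria be met before reoperation.

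Taken literally, the rule lets a later event change a status already observed. It would do so unevenly. Late reoperations would be recorded only for children whose families consented to the extension. The decision would be the unmasked surgeon's, which section 1.6 already recognises as a possible source of bias between arms. The same child could also be a failure AT 3 years in one analysis and not reoperated before 3 years in the 2018 tabulation.

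**Working it through.** The plan gives no figure that tests this point, so the main check compares texts. A short calculation then shows the scale.

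**1. Is there a time limit on the reoperation component?**

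| Place | Time limit |
|---|---|
| 2017 SAP 1.3 and Objective #2, masked-exam criteria | 6 months to 3 years |
| 2017 SAP 1.3 and Objective #2, reoperation or toxin | at any time during the study |
| 2017 SAP 1.6 | status at 3 years, with an undated exception for reoperation |
| 2017 SAP Objective #3, steps 1 and 6 | at any time |
| 2018 SAP 1.5 and Objective #4, reoperation item | in a list to be met at the 3-year visit |
| 2018 SAP Objective #4, no previous failure | at any time in the definition, by 3 years in the listed input |
| 2018 SAP 1.7, 3-year status | before 3 years |

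Only Objective #3 turns an undated reoperation into an explicit code for an outcome fixed at 3 years. The no-previous-failure version carries two conflicting statements. Its input traces to the patient-level failure variable of 2017 Objective #2 step 7, which is set to 1 for a reoperation at any month.

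**2. Who could be reclassified?** A child who completed the 3-year visit, met no criterion there, had no reoperation or toxin before it, was reoperated afterwards, and has that record in the treatment table.

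**3. Could such records be present?** The 2017 variables were built on pre-closeout data in January 2017, almost two years after Amendment II, and re-run on post-closeout data. The closeout database is dated 20 June 2017. A child randomised by 20 June 2013 had reached 4 years by then. The documents give no randomisation dates, and neither SAP says whether extension records were left out.

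**4. Are the Kaplan-Meier analyses affected?** Step 7 times a reoperation in months from surgery. One at month 45, say, has an event time after 36 and is not an event in the estimate read at month 36. The same holds for reoperation by 3 years (Objective #4).

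**5. Scale.** Each reclassified child adds 1/n to the proportion failing in that arm. Completers per arm are not stated. Assuming 80 to 95:
- 1/95 = 1.05 percentage points
- 1/80 = 1.25 percentage points

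For the treatment difference, assume that 80% or 90% of the 101 BLR and 96 R/R children complete the visit (81 and 77, or 91 and 86), with true failure of 25% or 35% in both arms. With f failures and k late reoperations, the difference is (f_B + k_B)/n_B − (f_R + k_R)/n_R. For example, at 80% completion and 25% failure, f_B = 20 and f_R = 19. Five late reoperations in BLR and none in R/R give 25/81 − 19/77 = 0.309 − 0.247 = 0.062.

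| Late reoperations, BLR / R/R | Difference over the four settings (points) | Fisher p |
|---|---|---|
| 1/1 or 2/2 | −0.6 to +0.2 | 1.0 |
| 5/0 | 5.2 to 6.2 | 0.44 to 0.51 |
| 10/0 | 10.7 to 12.4 | 0.12 to 0.17 |

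These counts are illustrative. The documents do not give the number of late reoperations.

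**The case against.** The best defence is that the phrase means up to 3 years in this document. The 2017 SAP is headed as a three-year analysis. Its Objective #4, reoperation by 3 years, uses the same phrase and calls reoperation without prior failure contrary to protocol, which is true only of the 3-year phase. Amendment II speaks of a 3-year study as distinct from the extension study. Objective #3 step 1 describes status as permanently set by reoperation before a missed 3-year visit, so it has earlier reoperations in mind. The manuscript database is labelled a 3-year closeout. The 2018 tabulation shows the cut-off the authors would probably choose.

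Most of this stands as evidence of intent, and it makes an actual error uncertain. It does not supply the missing limit. Step 6 says only at any time, the flag takes all visits, and a database label does not show which visits are inside. Amendment II also describes joining the extension as continuing study participation, so the word study does not settle the matter.

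The defence is right about the resolution outcomes. The reoperation item itself is anchored to the 3-year visit, and only the no-previous-failure version is ambiguous. It is also right that balanced late reoperations would hardly change the comparison.

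**Conclusion.** The point holds as a gap in a written coding rule for one secondary binary outcome, failure AT 3 years, together with an ambiguity in the 2018 resolution outcome with no previous failure. The harm is conditional: it needs extension treatment records in the source tables and at least one child reoperated after passing the 3-year exam. The size is unknown and may be zero. Under the assumed 80 to 95 completers per arm, it is about 1.05 to 1.25 percentage points in an arm per affected child.

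A reader might infer three stronger things that the documents do not support:
- That children were in fact misclassified. No late reoperation is reported, and the closeout label points the other way.
- That the primary result is compromised. Event timing protects the Kaplan-Meier estimates, provided they are read at 36 months.
- That the effect can be set against the difference of 8.6 points in the 2017 primary code (0.4594 − 0.3731 = 0.0863). That is a Kaplan-Meier difference for another outcome.

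**What to change.** - In 2017 SAP Objective #3 steps 1 and 6, count reoperation or botulinum toxin only if dated on or before the child's 3-year visit, using the date already carried forward in step 5.
- In 2018 SAP section 1.5 and Objective #4, apply the same limit to the reoperation item and to the previous-failure input, and replace at any time in the no-previous-failure definition so that it agrees with the by-3-years input.
- State whether the treatment tables hold extension visits, and that the Kaplan-Meier estimates are those at month 36.
- Re-run the flags and report how many children change. If none do, one sentence saying so closes the point.

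The cost is a few words in each SAP, one date condition on a stored variable and a re-run. No new data are needed.
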